14.4 Overall Disease Control Rate

The ODCR will be determined as the proportion of subjects who achieved CR, PR or SD as their best overall response during Treatment Period 2 in accordance with RECIST 1.1 criteria, relative to the efficacy population. The ODCR will be summarized by number and percentage of subjects meeting the definition of ODCR along with the corresponding exact 2-sided 95% confidence interval (CI). ODCR will not be calculated or presented for Treatment Period 1.

Since the study is closing early, no calculation of ODCR will be made.

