	
quintiles, number of valid cases for continuous variables and n, frequency and percentage for categorical variables with 95% confidence limits, when appropriate).
 
All subjects who received a full or partial dose of the study drug (in Treatment Period 2) on at least one occasion are considered evaluable subjects for safety analysis. All treated subjects in Treatment Period 2 who also undergo a CT or MRI scan with tumor assessment after 12 weeks, or who discontinue treatment prior to 12 weeks solely due to disease progression, will be included in the Full Analysis Set (FAS), which will be used for the efficacy evaluation. The Per Protocol population (all FAS subjects, excluding those for whom major protocol violations have been identified) will be used in the sensitivity analyses for all secondary efficacy endpoints.
 
The ODCR will be determined as the proportion of treated subjects who have achieved SD, PR or CR. The ORR will be determined as the proportion of treated subjects who have achieved CR or PR. Estimates of the ORR and the ODCR will be presented with the corresponding 95% confidence interval. PFS, duration of stable disease, and OS will be analyzed using the Kaplan-Meier method. The Kaplan-Meier survival curves will be plotted. OS is defined as the time from the first dose of study drug (beginning of Treatment Period 2) until the date of death from any cause. Subjects who do not die will be censored for this analysis at the last documented date at which the subject is known to be alive. PFS is defined as the time from the first dose of study drug (beginning of Treatment Period 2) until objective tumor progression or death. Medians for time to event variables will be presented with the corresponding 95% confidence intervals.

Interim Analysis	
Interim analysis will be performed for the primary efficacy endpoint (ODCR) once the first tumor assessment during Treatment Period 2 is completed for at least 20 enrolled subjects. An interim analysis of all efficacy endpoints (with the exclusion of overall survival) may also be performed once all enrolled subjects have entered the Follow-up Period and are being followed for overall survival. Analysis of all safety endpoints will also be included in any interim analyses.

Number of Study Centers (and Locations) Planned	
Up to 50 study sites in the US and Europe are planned for enrollment.

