7. STATISTICAL METHODOLOGY

7.1. Sample Size

The primary objective of the study is to evaluate the efficacy of the study drug by the frequency of subjects with overall disease control (including SD, PR, and CR).

The null hypothesis assumes an historical disease control rate of <5%, given that these subjects have already failed progestin therapy. A clinically significant difference is predefined as a 15% increase (i.e. disease control rate of 20%). Using the Fleming's single stage procedure (in which a predetermined number of patients is recruited to the study and a decision about activity is obtained from the number of responses (including SD, PR, or CR) amongst these patients) with the probabilities of type I and type II errors of 5% (one-sided) and 10%, respectively, approximately 40 subjects are planned to be enrolled to Treatment Period 2. It is estimated that approximately 20-25% of subjects will be classified as PrR negative and go directly into Treatment Period 2. This group will represent 14-16 of the Treatment Period 2 subjects. The rate of subjects who will have progressive disease following treatment with megestrol acetate in Treatment Period 1 and then move on to Treatment Period 2 is estimated at 55-60%. These subjects will represent 30-32 of the Treatment Period 2 subjects (estimating that approximately 24-25 subjects treated in Treatment Period 1 will not exhibit progressive disease and will not move into Treatment Period 2.) Estimating the rate of subjects who will be unavailable for disease assessment for various reasons at 10-15%, it is planned to enroll 72 total subjects. An estimated 20% screen failure rate will require up to 90 screened patients to allow for enrollment of 72 subjects.

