7.4.1. Analysis of Primary Objective

The primary objective of this study is to evaluate the efficacy of the study drug by the frequency of subjects with overall disease control (including SD, PR, and CR).

The ODCR will be determined as the proportion of subjects who achieved SD, PR and CR during Treatment Period 2. The ODCR will be estimated and presented with the corresponding 95% confidence interval.

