5.3 Dose Modifications

There will be no allowed modifications to the dosage, including dose reduction, of either MA or SC during the trial.

If an injection of SC is not administered on the scheduled dosing date, this can be done during the next two days but no later than 1 day before the next scheduled dose. The subsequent injection of SC should be given in accordance with the study drug administration schedule. If a subject misses a dose of MA, the next dose should be taken at the regularly scheduled time.

SC and MA combination therapy should be discontinued if an AE of Grade 3 or higher (in accordance with NCI-CTCAE [National Cancer Institute-Common Terminology Criteria for Adverse Events] Version 4.03 criteria) is observed and determined to be potentially related to either medication. When combination treatment is discontinued, both SC and MA are to be discontinued. Monotherapy in Treatment Period 2 is not permitted. The treatment will not be re-started and the subject will be withdrawn from Treatment Period 2 and enter the Follow-Up Period.

6. Sample Size and Power Considerations

The primary objective of the study is to evaluate the efficacy of the study drug by the frequency of subjects with overall disease control (CR, PR and SD). The null hypothesis assumes an historical disease control rate of < 5%, given that these subjects have already failed progestin therapy. A clinically significant difference is predefined as a 15% increase (i.e. disease control rate of 20%). Using A'Hern's update of Fleming's single stage procedure (in which a predetermined number of subjects is recruited to the study and a decision about activity is obtained from the number of responses [including CR, PR] and SD amongst these subjects) with the probabilities of type I and type II errors of 5% (one-sided) and 10%, respectively, approximately 40 subjects are needed to contribute to the primary analysis in

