9.2 Missing Data and Adjustments for Multiplicity

This is a phase 2, exploratory study. Missing values will not be estimated. All data will be included in safety analysis. Censoring rules for time to event analyses are described in Section 14. Since no

statistical testing will be performed, there will be no adjustments for multiplicity. Fleming's procedure is based on a one sample hypothesis test for a proportion. Because there is a single primary hypothesis, treatment corrections for multiplicity are not required.

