14.5 Overall Response Rate

The ORR is defined as the proportion of subjects who achieved CR or PR as their best overall response during Treatment Period 2 in accordance with RECIST 1.1 criteria, relative to the efficacy population. Subjects who do not have an on-study assessment due to safety issues will be included as non-responders. The ORR will be summarized by number and percentage of subjects meeting the definition of ORR along with the corresponding exact 2-sided 95% CI. The ORR will not be calculated or presented for Treatment Period 1.

Since the study is closing early, no calculation of ORR will be made.

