2. The primary efficacy endpoint ODCR and secondary efficacy endpoint ORR will not be assessed.
3. Protocol 7.7 indicates that protocol deviations will be collected on the eCRFs. Instead, deviations will be collected and monitored by the site monitors and transferred to SDC as an Excel spreadsheet.

Any changes to the planned analyses after database lock and unblinding will be described in the clinical study report.

21. References

R. P. A'Hern. Sample size tables for exact single-stage phase II designs. *Statist. Med.* 2001; 20:859:866.

Fleming TR. One sample multiple testing procedure for phase II clinical trials. *Biometrics* 1982; 38:143:151.

22. Revision History

Documentation of revision to the SAP will commence after approval of the Final version 1.0.

23. Tables

14.3.3.7	Electrocardiogram QTcB and QTcF Categories	Safety Population
----------	--	-------------------

24. Figures

14.2.1.1	Swimmer's Plot of Treatment and Response Durations	Safety Population Population – Subjects who Participated in Treatment Period 2
----------	--	---

25. Listings

Listing Number	Title	Population
16.2.1.1	Subject Disposition	All Enrolled Subjects
16.2.1.2	Screen Failures	All Screened Subjects
16.2.1.3	Informed Consent	All Enrolled Subjects
16.2.1.4	Visit Dates	All Enrolled Subjects
16.2.1.5	Inclusion and Exclusion	All Enrolled Subjects
16.2.2	Protocol Deviations	All Enrolled Subjects
16.2.3	Analysis and Treatment Period Populations	All Enrolled Subjects
16.2.4.1	Demographics and Baseline Characteristics	Safety Population
16.2.4.2	Baseline Disease Characteristics and PrR Status	Safety Population
16.2.4.3	Medical and Surgical History	Safety Population
16.2.4.4	Prior and Concomitant Medications	Safety Population
16.2.4.5.1	Prior Chemotherapy	Safety Population
16.2.4.5.2	Prior Hormonal Therapy	Safety Population
16.2.4.5.3	Prior Radiotherapy	Safety Population
16.2.4.5.4	Prior Cancer Surgery	Safety Population
16.2.4.6	Pregnancy Test Results	Safety Population
16.2.5.1	Sodium Cridanimod Administration	Safety Population

Listing Number	Title	Population
16.2.5.2	Megestrol Acetate Diary	Safety Population
16.2.5.3	Megestrol Acetate Accountability	Safety Population
16.2.6.1	Investigator Target Lesion Assessments by Visit	Full Analysis Set
16.2.6.2	Summary of Investigator Target Lesion Assessments and New Lesions by Visit	Full Analysis Set
16.2.6.3	Investigator Non-Target Lesion Assessments by Visit	Full Analysis Set
16.2.6.4	Best Overall Response	Full Analysis Set

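### The SAP promises efficacy results for every Treatment Period 2 subject but limits the listings to the FAS; descriptive ODCR and ORR could also be kept at little cost

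*SAP*

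**What the plan says.** **Who is to be shown.** The opening of SAP section 14 says that best overall response, PFS, OS and, where applicable, duration of stable disease will be listed for each subject in Treatment Period 2. Sections 14.6, 14.7 and 14.8 repeat this for duration of stable disease, PFS and OS. Section 14.3 determines best response for every Period 2 participant and plans a swimmer's plot of all Safety Population subjects in that period.

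The list of listings in section 25 gives the population for 16.2.6.4 (best overall response) as the Full Analysis Set, and for 16.2.6.5 to 16.2.6.7 (duration of stable disease, PFS, OS) as the Full Analysis Set in Treatment Period 2. The lesion listings 16.2.6.1 to 16.2.6.3 are also FAS. Under section 8.2, a Period 2 subject is in the FAS only with a Week 12 tumor assessment, or if she stopped earlier solely because of documented progression.

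**What happens to the rates.** Protocol 7.4.1 plans an estimate: "The ODCR will be estimated and presented with the corresponding 95% confidence interval". SAP 14.4 and 14.5 define both rates with number, percentage and exact two-sided 95% interval, then withdraw them: "Since the study is closing early, no calculation of ODCR will be made" and "Since the study is closing early, no calculation of ORR will be made". SAP section 20 declares this as a change from the protocol: "The primary efficacy endpoint ODCR and secondary efficacy endpoint ORR will not be assessed".

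**What the decision rule needed.** In the single-stage procedure of protocol 7.1, "a decision about activity is obtained from the number of responses". SAP section 6 says that "approximately 40 subjects are needed to contribute to the primary analysis in" Treatment Period 2. Section 4.5 reports 25 women enrolled at closing.

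**The concern.** In an abbreviated report made up almost entirely of listings, the population of a listing decides which subjects a reader can see. The FAS restriction removes a particular kind of subject: one who leaves Period 2 before Week 12 through toxicity, withdrawal, death without documented progression, or the closure itself. That is not a random subset, and section 14 says these subjects will be listed.

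The second issue is smaller. The reason given for dropping ODCR and ORR is early closure. That reason fits the go/no-go decision, but not a proportion with an interval. Without the proportion, the report has no pre-specified summary of the primary endpoint, although best response is still derived subject by subject.

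**Working it through.** **1. Text against output list**

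| Result | Promised for | Listing population |
|---|---|---|
| Best overall response | each Period 2 subject (14) | FAS (16.2.6.4) |
| Duration of stable disease, where applicable | each Period 2 subject (14, 14.6) | FAS (16.2.6.5) |
| PFS | each Period 2 subject (14, 14.7) | FAS (16.2.6.6) |
| OS | each Period 2 subject (14, 14.8) | FAS (16.2.6.7) |

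Take a subject who dies in Week 8 of Period 2 with no documented progression. Under 14.7 and 14.8 she is a PFS event and an OS event. Under 8.2 she is outside the FAS, so she is in neither 16.2.6.6 nor 16.2.6.7. Her death is in Listing 16.2.7.7 (Mortality, Safety Population). Her best response is only in the swimmer's plot.

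**2. How many subjects this could touch**

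The Period 2 count is not in the documents, so this is an assumption built from the planning rates in SAP section 6: 20–25% PrR negative, 55–60% of the rest progressing, 10–15% not assessable. Dosed in Period 2 = 25 × [f + (1 − f) × p]:

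- f = 0.20, p = 0.55: 25 × (0.20 + 0.44) = 16.0
- f = 0.20, p = 0.60: 25 × (0.20 + 0.48) = 17.0
- f = 0.25, p = 0.55: 25 × (0.25 + 0.4125) ≈ 16.6
- f = 0.25, p = 0.60: 25 × (0.25 + 0.45) = 17.5
- from the planned counts, 14 + 30 = 44 to 16 + 32 = 48 of 72: 25 × 44/72 = 15.3 to 25 × 48/72 = 16.7

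Not assessable: 16.0 × 0.10 = 1.6 to 17.5 × 0.15 = 2.6, so about two. The closure could make Period 2 smaller and the loss larger.

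**3. The planned decision, reproduced**

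Exact binomial, null rate 5%, alternative 20%, one-sided alpha at most 0.05, power at least 0.90. The smallest design is n = 38 with at least 5 controlled (alpha 0.040, power 0.901). At n = 40 with the same cut-off, alpha is 0.048 and power 0.924. This agrees with the plan's figure of about 40.

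At the assumed sizes:

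| n | Cut-off | Alpha | Power at 20% |
|---|---|---|---|
| 15 | 3 | 0.036 | 0.602 |
| 16 | 3 | 0.043 | 0.648 |
| 17 | 4 | 0.009 | 0.451 |

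The decision rule is lost.

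**4. The descriptive estimate** (exact Clopper-Pearson 95% intervals, assumed counts)

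| x/N | Rate | 95% CI |
|---|---|---|
| 0/16 | 0% | 0–20.6% |
| 3/16 | 18.8% | 4.0–45.6% |
| 2/10 | 20.0% | 2.5–55.6% |
| 8/40 (planned size) | 20.0% | 9.1–35.6% |

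The interval is wide but carries information. For a subgroup of five it carries little: 1/5 gives 0.5–71.6%.

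**5. FAS against all dosed**

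Suppose 16 are dosed, 14 are in the FAS and 3 of those 14 are controlled. The FAS rate is 3/14 = 21.4% (4.7–50.8%).

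- If neither of the two outside the FAS is controlled, the all-dosed rate is 3/16 = 18.8%, which is lower.
- If one of them had stable disease on an unscheduled scan (section 14 allows such scans, and 14.2 asks for only 6 weeks) and then stopped before Week 12 for an adverse event, it is 4/16 = 25.0%, which is higher.

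**The case against.** The cancellation is open. The SAP gives the reason several times, records the change in section 20, says that it supersedes the protocol's methods, and allows further analyses if the study report identifies them. Tabulating a rate from so few subjects in a closed trial is a matter of judgement. This stands, and so the rate is only the secondary part here.

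Three stronger readings are tempting, and the documents do not support them.

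- *A reader might infer that no denominator is named.* The undefined term efficacy population in 14.4 and 14.5 invites this, as does the synopsis: "The ODCR will be determined as the proportion of treated subjects who have achieved SD, PR or CR". But the synopsis also names the FAS for the efficacy evaluation, as do protocol 7.2.2 and 7.4 and SAP 8.2. The intended set is clear and the wording is loose.
- *A reader might infer that subjects outside the FAS vanish from the report except for the plot.* They remain in the disposition, population and Sodium Cridanimod administration listings where applicable (16.2.1.1, 16.2.3, 16.2.5.1), and deaths are in 16.2.7.7. Only their best response is confined to the plot.
- *A reader might infer that the FAS rate must be the more favorable one.* Step 5 shows that it can go either way.

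None of this answers the mismatch between section 14 and the listing populations.

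**Conclusion.** The mismatch is wrong as written. Sections 14 and 14.6 to 14.8 promise results for each Period 2 subject, while Listings 16.2.6.4 to 16.2.6.7 cover a set that drops early stoppers without documented progression. Under the planning rates about two of roughly 15 to 17.5 dosed subjects would be affected. Both numbers are assumptions, since the documents give only the 25 enrolled, and the range is not a bound.

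Keeping ODCR and ORR as descriptive summaries is a cheap improvement, not the correction of an error. SAP 9.2 itself says that the Fleming "procedure is based on a one sample hypothesis test for a proportion", and that test is what early closure removes. A proportion with an exact interval fits the SAP's statement in 3.5 that no formal testing is planned. The illustrative counts support no conclusion about the 5% or 20% rates.

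**What to change.** **Listings (the main change).** Set 16.2.6.4 to 16.2.6.7 to all subjects dosed in Treatment Period 2, with an FAS flag. Do the same for the lesion listings 16.2.6.1 to 16.2.6.3, so that each listed response has its measurements behind it.

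**Rates (secondary).** In 14.4, 14.5 and 20, with matching edits in 2, 3.1, 6, 14 and the table list, replace the cancellation with text such as: *ODCR and ORR are reported descriptively as n/N with exact two-sided 95% CI, pooled and without a test, in the FAS and, beside it, in all subjects dosed in Treatment Period 2. Subjects whose best response is NE, or who have no on-study assessment, stay in the denominator as not controlled or non-responders, and their reasons are shown.*

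- Replace the term efficacy population with these two named sets.
- Apply the 14.5 sentence on subjects unassessed for safety issues to the all-dosed set, since the FAS can exclude them.
- Give the Period 2 reporting groups of 9.6 as counts only.

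**Housekeeping.** Delete the Kaplan-Meier and PPS paragraph in 14.8. It conflicts with 8.3, with 14.6 and 14.7, with the last paragraph of 14.8 and with the output lists.

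**Cost.** One small table and seven listings change, with no new data collection. The intervals will be wide. The all-dosed rate is conservative for subjects left unassessed by the closure, so the table must be labelled descriptive. The Period 2 discontinuation reasons in 10.1 have no sponsor-termination category, so that reason may be visible only where it was recorded under Other.

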14.5 Overall Response Rate

The ORR is defined as the proportion of subjects who achieved CR or PR as their best overall response during Treatment Period 2 in accordance with RECIST 1.1 criteria, relative to the efficacy population. Subjects who do not have an on-study assessment due to safety issues will be included as non-responders. The ORR will be summarized by number and percentage of subjects meeting the definition of ORR along with the corresponding exact 2-sided 95% CI. The ORR will not be calculated or presented for Treatment Period 1.

Since the study is closing early, no calculation of ORR will be made.

14.6 Duration of Stable Disease

Duration of SD is defined for all subjects whose best overall response is SD as the number of days from the date of the first doses of combination therapy on Study Visit 1, Day 0-TP2 in Treatment Period 2 to the first date of disease progression or death due to disease under study (date of progression or death due to disease under study – date of first dose of combination therapy). For subjects who die from causes other than disease under study, duration of SD will be censored at the date of death. For those subjects who discontinue from the study for reasons other than disease progression or death, duration of SD will be censored at the date of the last disease assessment prior to study discontinuation.

Duration of SD will not be calculated or presented for Treatment Period 1. Duration of SD will be listed for individual subjects in Treatment Period 2, but no median duration of SD will be calculated.

14.7 Progression-Free Survival

PFS is defined as the number of days between the date of the first doses of combination therapy on Study Visit 1, Day 0-TP2 in Treatment Period 2 and the first date of disease progression or death from any cause (date of progression or death – date of first dose of study drug + 1). For those subjects who discontinue from the study for reasons other than disease progression or death, including subjects for whom best overall response cannot be determined, PFS will be censored at the date of the last Treatment Period 2 disease assessment prior to study discontinuation (EOS).

PFS will not be calculated or presented for Treatment Period 1. PFS will be listed for individual subjects in Treatment Period 2, but no median PFS will be calculated.

14.8 Overall Survival

OS is defined as the number days between the date of the first doses of combination therapy on Study Visit 1, Day –TP2 in Treatment Period 2 and the date of death from any cause. For those subjects who discontinue from the study for reasons other than death, OS will be censored at the date of last contact.

PFS, Duration of SD, and OS will be analyzed by Kaplan-Meier methods. The estimated survival and probabilities will be presented via Kaplan-Meier curves and median survival/duration including exact 2-sided 95% CI will be reported using both the FAS and the PPS.

OS will not be calculated or presented for Treatment Period 1. OS will be listed for individual subjects in Treatment Period 2, but no median OS will be calculated.

15. Safety Analyses

15.1 Adverse Events

An AE is any untoward medical occurrence in a subject or clinical investigation subject administered a pharmaceutical product that does not necessarily have a causal relationship with this treatment. An AE can therefore be any unfavorable and unintended sign (including a clinically significant abnormal laboratory finding), symptom or disease temporally associated with the use of a pharmaceutical product, whether or not considered related to the pharmaceutical product. AEs may include the onset of new illness and the exacerbation of pre-existing conditions.

For the purposes of this protocol, an AE is any undesirable sign(s), symptom(s) or worsening of pre-existing condition(s) occurring after the signing of the informed consent through the final study visit, even if the event is not considered to be related to the study drug. No AEs information will be collected following the Safety Follow-Up Visit. The nature of each AE, date of onset, outcome, severity, actions taken with respect to dosage, and relationship to study drug will be assessed and recorded.

An AE is “unexpected” when the nature, severity, specificity, or outcome is not consistent with the term or description used in protocol related documents including the Investigator brochure, product labeling

(e.g. Package Insert or Summary of Product Characteristics), protocol and Independent Ethics Committee (IEC)/ Institutional Review Board (IRB) approved informed consent form. If an Investigator is uncertain whether an AE is expected or unexpected, the AE should be reported as unexpected.

The outcome of each AE should be assessed as follows:

- Fatal: Subject has died due to AE
- Not Recovered/Not Resolved: AE is ongoing
- Recovered/Resolved: AE is no longer present
- Recovered/Resolved with sequelae: AE has resolved but the subject retains a condition that is the consequence of the AE
- Recovered/Resolving: AE is in the process of recovering
- Unknown: Outcome of the AE is not known because the subject did not return for follow-up and attempts to obtain follow-up were unsuccessful

The causality of each AE, with respect to each study drug separately, should be assessed using one of the following terms:

- Related: AE occurring in a plausible time relationship to drug administration, and which cannot be explained by concurrent disease or other drugs or chemicals.
- Possibly Related: AE occurring with a reasonable time sequence to administration of the drug, unlikely to be attributed to concurrent disease or other drugs or chemicals.
- Unlikely Related: AE occurring with a reasonable time sequence to administration of the drug, but which could also be explained by concurrent disease or other drugs or chemicals.
- Not Related: AE with a temporal relationship to drug administration which makes a causal relationship improbable, and in which other drugs, chemicals or underlying disease provide plausible explanations.

For data analysis and Serious Adverse Event (SAE) reporting purposes, any AEs classified as 'unlikely related' will be regarded as 'not related' to study drug. AEs classified as 'possibly related' will be regarded as 'related' to the study drug.

The severity of all AEs should be graded in accordance with the NCI-CTCAE Version 4:

- 1 – Mild: Does not hamper daily activities
- 2 – Moderate: Hampers daily activities

3 – Severe: Makes daily activities impossible

4 – Life-Threatening: Imminent risk of death

5 – Death

Disease progression or symptoms related to disease progression will not be considered AEs.

